PR	PD	SD provided minimum criteria for SD duration met, otherwise, PD
PR	NE	SD provided minimum criteria for SD duration met, otherwise NE
NE	NE	NE

CR = complete response, PR = partial response, SD = stable disease, PD = progressive disease, and NE = Not evaluable.

¹ If a CR is truly met at first time point, then any disease seen at a subsequent time point, even disease meeting PR criteria relative to baseline, makes the disease PD at that point (since disease must have reappeared after CR). Best response would depend on whether minimum duration for SD was met. However, sometimes CR' may be claimed when subsequent scans suggest small lesions were likely still present and in fact the patient had PR, not CR at the first time point. Under these circumstances, the original CR should be changed to PR and the best response is PR.

Special notes on response assessment

When nodal disease is included in the sum of target lesions and the nodes decrease to 'normal' size (< 10 mm), they may still have a measurement reported on scans. This measurement should be recorded even though the nodes are normal in order not to overstate progression should it be based on increase in size of the nodes. As noted earlier, this means that patients with CR may not have a total sum of 'zero' on the case report form (CRF).

In trials where confirmation of response is required, repeated 'NE' time point assessments may complicate best response determination. The analysis plan for the trial must address how missing data/assessments will be addressed in determination of response and progression. For example, in most trials it is reasonable to consider a patient with time point responses of PR-NE-PR as a confirmed response.

Patients with a global deterioration of health status requiring discontinuation of treatment without objective evidence of disease progression at that time should be reported as 'symptomatic deterioration'. Every effort should be made to document objective progression even after discontinuation of treatment. Symptomatic deterioration is not a descriptor of an objective response: it is a reason for stopping study therapy. The objective response status of such patients is to be determined by evaluation of target and non-target disease as shown in Tables 1–3.

Conditions that define 'early progression, early death and inevaluable' are study specific and should be clearly described in each protocol (depending on treatment duration, treatment periodicity).

In some circumstances it may be difficult to distinguish residual disease from normal tissue. When the evaluation of complete response depends upon this determination, it is recommended that the residual lesion be investigated (fine needle aspirate/biopsy) before assigning a status of complete response. FDG-PET may be used to upgrade a response to a CR in a manner similar to a biopsy in cases where a residual radiographic abnormality is thought to represent fibrosis or scarring. The use of FDG-PET in this circumstance should be prospectively described in the protocol and supported by disease specific medical literature for the indication. However, it must be acknowledged that both approaches may lead to false positive CR due to limitations of FDG-PET and biopsy resolution/sensitivity.

For equivocal findings of progression (*e.g.* very small and uncertain new lesions; cystic changes or necrosis in existing lesions), treatment may continue until the next scheduled assessment. If at the next scheduled assessment, progression is confirmed, the date of progression should be the earlier date when progression was suspected.

Frequency of tumor re-evaluation

Frequency of tumor re-evaluation while on treatment should be protocol specific and adapted to the type and schedule of treatment. However, in the context of phase II studies where the beneficial effect of therapy is not known, follow-up every 6–8 weeks (timed to coincide with the end of a cycle) is reasonable. Smaller or greater time intervals than these could be justified in specific regimens or circumstances. The protocol should specify which organ sites are to be evaluated at baseline (usually those most likely to be involved with metastatic disease for the tumor type under study) and how often evaluations are repeated. Normally, all target and non-target sites are evaluated at each assessment. In selected circumstances certain non-target organs may be evaluated less frequently. For example, bone scans may need to be repeated only when complete response is identified in target disease or when progression in bone is suspected. After the end of the treatment, the need for repetitive tumor evaluations depends on whether the trial has as a goal the response rate or the time to an event (progression/death). If 'time to an event' (*e.g.* time to progression, disease-free survival, progression-free survival) is the main endpoint of the study, then routine scheduled re-evaluation of protocol specified sites of disease is warranted. In randomised comparative trials in particular, the scheduled assessments should be performed as identified on a calendar schedule (for example: every 6–8 weeks on treatment or every 3–4 months after treatment) and should not be affected by delays in therapy, drug holidays or any other events that might lead to imbalance in a treatment arm in the timing of disease assessment.

Confirmatory measurement/duration of response

Confirmation

In non-randomised trials where response is the primary endpoint, confirmation of PR and CR is required to ensure responses identified are not the result of measurement error. This will also permit appropriate interpretation of results in the context of historical data where response has traditionally required confirmation in such trials. However, in all other circumstances, *i.e.* in randomised trials (phase II or III) or studies where stable disease or progression are the primary endpoints, confirmation of response is not required since it will not add value to the interpretation of trial results. However, elimination of the requirement for response confirmation may increase the importance of central review to protect against bias, in particular in studies which are not blinded.

In the case of SD, measurements must have met the SD criteria at least once after study entry at a minimum interval (in general not less than 6–8 weeks) that is defined in the study protocol.

Duration of overall response

The duration of overall response is measured from the time measurement criteria are first met for CR/PR (whichever is first recorded) until the first date that recurrent or progressive disease is objectively documented (taking as reference for progressive disease the smallest measurements recorded on study).

The duration of overall complete response is measured from the time measurement criteria are first met for CR until the first date that recurrent disease is objectively documented.

Duration of stable disease

Stable disease is measured from the start of the treatment (in randomised trials, from date of randomisation) until the criteria for progression are met, taking as reference the smallest sum on study (if the baseline sum is the smallest, this is the reference for calculation of PD).

The clinical relevance of the duration of stable disease varies in different studies and diseases. If the proportion of patients achieving stable disease for a minimum period of time is an endpoint of importance in a particular trial, the protocol should specify the minimal time interval required between two measurements for determination of stable disease.

Note: The duration of response and stable disease as well as the progression-free survival are influenced by the frequency of follow-up after baseline evaluation. It is not in the scope of this guideline to define a standard follow-up frequency. The frequency should take into account many parameters including disease types and stages, treatment periodicity and standard practice. However, these limitations of the precision of the measured endpoint should be taken into account if comparisons between trials are to be made.

Appendix 4: Instructions to Investigator for handling data rights requests

DATA PROTECTION / GDPR (General Data Protection Regulation of 27 April 2016 n°2016/679)

INSTRUCTIONS TO INVESTIGATOR FOR HANDLING DATA RIGHTS REQUESTS

In the framework of a research study/clinical trial, a participant to the study may exercise his/her rights, i.e. may ask IRIS (as data controller) for:

- access to his/her data
- rectification of inaccurate/incomplete information
- restriction of processing of data
- objection to processing of data
- data portability (receiving his/her data in a readable format)

In accordance with the Informed Consent Form and information notice provided to participant, we requested participant to contact you first for exercising their rights.

Request for exercise of rights:

- has to be a **written** one (either originating from an (e)-mail from a participant or from request expressed orally to you and put in written)
- has to be sent **by you** by e-mail or by mail **to** IRIS (as data controller) to central address [contact] or local Servier address as mentioned in ICF/information notice provided/available

DO Instructions to be followed by you	DON'T What you should not do
E-mail title: Data protection rights	Do not forward participant e-mail (if applicable)
Study name/number	
Participant number	No information regarding participant identity: No participant's name, e-mail address, participant's signature
As soon as possible without exceeding a week	

IRIS and INVESTIGATOR responsibilities**GDPR requirement:**

It is mandatory for IRIS as data controller to provide an answer to participant/volunteer within 1 month following the request (article 12 of GDPR)

Clinical trials requirements:

It is prohibited for IRIS as a Sponsor to know the identity of the participants/volunteer participating to studies

	IRIS responsibility	Investigator responsibility
Forward/inform IRIS of the request		YES
Timelines	Answer within 1 month once expressed by the participant	Request: transmitted to IRIS as soon as expressed by the participant Answer: transmitted by you to participant as soon as sent by IRIS
Answer the request	YES	

Appendix 5: Eastern Cooperative Oncology Group Performance Status Scoring

Grade	Symptomatology
0	Fully active, able to carry on all pre-disease performance without restriction
1	Restricted in physically strenuous activity but ambulatory and able to carry out work of a light or sedentary nature, eg, light house work, office work
2	Ambulatory and capable of all self-care but unable to carry out any work activities. Up and about more than 50% of waking hours
3	Capable of only limited self-care, confined to bed or chair more than 50% of waking hours
4	Completely disabled. Cannot carry on any self-care. Totally confined to bed or chair
5	Dead

Source: Oken MM, Creech RH, Tormey DC, Horton J, Davis TE, McFadden ET, et al. Toxicity and Response Criteria of the Eastern Cooperative Oncology Group. *Am J Clin Oncol* 1982;5:649-655.

Appendix 6: Prohibited Concomitant Medications

Prohibited medications and certain foods are not allowed in this study while subjects are receiving study drug.	
Strong CYP3A Inducers	CYP3A Substrates with a Narrow Therapeutic Window
Avasimibe, carbamazepine, enzalutamide, mitotane, phenytoin, rifampin, rifabutin, St. John's wort	Alfentanil, astemizole ¹ , cyclosporine, dihydroergotamine, ergotamine, fentanyl, pimozide, quinidine, everolimus, sirolimus, tacrolimus, terfenadine ¹

Note that this is not an exhaustive list. For an updated list, see the following link:
<http://www.fda.gov/Drugs/DevelopmentApprovalProcess/DevelopmentResources/DrugInteractionsLabeling/ucm080499.htm>

“CYP substrates with a narrow therapeutic window” refers to drugs whose exposure-response relationship indicates that small increases in their exposure levels by the concomitant use of CYP inhibitors may lead to serious safety concerns (eg, Torsades de Pointes).

¹ Withdrawn from the United States market because of safety reasons.

Appendix 7: New York Heart Association Classification

Class	Symptomatology
I	No limitation of physical activity. Ordinary physical activity does not cause undue fatigue, palpitation, dyspnea, or anginal pain.
II	Slight limitation of physical activity. Comfortable at rest, but ordinary physical activity results in fatigue, palpitation, dyspnea, or anginal pain.
III	Marked limitation of physical activity. Comfortable at rest, but less than ordinary activity results in fatigue, palpitation, dyspnea, or anginal pain.
IV	Unable to carry on any physical activity without discomfort. Symptoms at rest. If any physical activity is undertaken, discomfort is increased.

Source: The Criteria Committee of the New York Heart Association. Nomenclature and Criteria for Diagnosis of Diseases of the Heart and Great Vessels. 9th ed. Boston, Mass: Little, Brown & Co; 1994:253-256.

Appendix 8: Fridericia's Formula

$$QTcF = QT/RR^{1/3}$$

Appendix 9: Medications Known to Prolong the QT Interval

amiodarone	dofetilide	grepafloxacin	moxifloxacin	quinidine
astemizole	dolasetron	halofantrine	norfloxacin	sevoflurane
azithromycin	domperidone	haloperidol	ofloxacin	sotalol
bepridil	droperidol	ibutilide	ondansetron	sparfloxacin
chloroquine	erythromycin	itraconazole	palonosetron	terfenadine
chlorpromazine	escitalopram	ketoconazole	pentamidine	thioridazine
ciprofloxacin	flecainide	levofloxacin	pimozide	voriconazole
citalopram	gatifloxacin	levomethadyl	posaconazole	
clarithromycin	gemifloxacin	mesoridazine	probucol	
disopyramide	granisetron	methadone	procainamide	

For a complete and updated (ongoing) list of medications, please use the following link:
<https://crediblemeds.org/healthcare-providers/>

Appendix 10: Examples of Strong and Moderate CYP3A4 Inhibitors

Moderate CYP3A4 Inhibitors
Aprepitant, cimetidine, ciprofloxacin, clotrimazole, crizotinib, cyclosporine, dronedarone, erythromycin, fluconazole, fluvoxamine, imatinib, tofisopam, verapamil
Strong CYP3A4 Inhibitors
Boceprevir, clarithromycin, conivaptan, grapefruit juice, indinavir, itraconazole
Ketoconazole, lopinavir/ritonavir, mibefradil, nefazodone, neflunavir, posaconazole
Ritonavir, saquinavir, telaprevir, telithromycin, voriconazole

Note: Based on FDA guidelines; Investigators should follow local institutional guidelines, where appropriate.

Appendix 11: Representative Examples of Low-Fat and High-Fat, High-Calorie Meals

Low-fat breakfast:

A) 2 slices of white bread toast, 1 tablespoon light fat margarine, 1 tablespoon of jelly, and 8 ounces of skim milk (319 calories and 8.2 grams of fat).

B) 1 cup of cereal, 1 slice of toast with jam, 8 ounces of skim milk, and 1 cup of decaffeinated coffee or tea (520 calories and 2 grams of fat).

A high-fat breakfast consists of the following and may be adapted to the local regional preference: 2 eggs fried in butter, 2 strips of bacon, 2 slices of white bread with butter, 1 croissant with 1 slice of cheese, and 8 ounces of whole milk. This representative high-fat breakfast contains approximately 1000 calories and 58 grams of fat.

**Follow up of versions**

Version	Release date (dd/mm/yyyy)	Key change(s) (*)	Protocol version associated	Rationale
1.0	8/3/2024	Not applicable	1.0 Non-substantial amendment no.1, no.2 and no.3	Not applicable

(\*) Key changes as compared to the statistical analyses planned in the protocol for the first SAP signed version (1.0). Key changes from the previous signed version for the other SAP signed version(s). See also [section 7](#) for the changes to protocol-planned analyses.

### List of abbreviations

AE	: Adverse event
ALP	: Alkaline phosphatase
ALT	: Alanine aminotransferase
AST	: Aspartate aminotransferase
BOR	: Best overall response
BUN	: Blood urea nitrogen
C1D1	: Cycle 1, Day 1
CR	: Complete response
CSP	: Clinical study protocol
CTCAE	: Common Terminology Criteria for Adverse Events
DOE	: Duration of response
ECOG	: Eastern Cooperative Oncology Group
EORTC	: European Organisation for Research and Treatment of Cancer
EOT	: End of treatment
HRQOL	: Health-related quality of life
IDH	: Isocitrate dehydrogenase protein
IRC	: Independent Radiology Center
ITT	: Intent-to-Treat
LDH	: Lactate dehydrogenase
LVEF	: Left ventricular ejection fraction
NCI	: National Cancer Institute
OR	: Objective response
OS	: Overall survival
PAS	: Pharmacokinetic Analysis Set
PD	: Progressive disease
PFS	: Progression-free survival
PK	: Pharmacokinetic
PPS	: Per-Protocol Set
PR	: Partial response
PT	: Preferred Term, Preferred Term
QD	: Once daily
QLQ-BIL21	Quality Of Life Questionnaire - Cholangiocarcinoma and Gallbladder Cancer Module
QLQ-C30	Quality of Life Questionnaire - Core Questionnaire
RBC	: Red blood cell
RECIST	: Response Evaluation Criteria in Solid Tumors
SAE	: Serious adverse event
SAS	: Safety Analysis Set
SD	: Standard deviation, Stable disease
SMQ	: Standardized MedDRA Query
SOC	: System Organ Class, System Organ Class
TEAE	: Treatment-emergent adverse event
TLG	: Tables, Listings and Graphs
TTR	: Time to response
ULN	: Upper limit of normal
WBC	: White blood cell

## 1. INTRODUCTION

This Statistical Analysis Plan details the planned analyses to be performed, in accordance with the main characteristics of the study protocol version 1.0 dated from 20/03/2023, non-substantial protocol amendment 1 dated from 24/05/2023, non-substantial protocol amendment 2 dated from 29/06/2023 and non-substantial protocol amendment 3 dated from 13/02/2024. The primary analyses will be performed approximately 6 months after the last subject enrolled for the 6-month PFS rate assessment. The additional analyses will be performed at the end of the study.

The templates for Tables, Listings and Graphs (TLG) are described in a separate document.

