Study period: - Study initiation date: Sep 2023 (FVFP) - Study completion date: Estimated May 2027	Study development phase: Phase II								
Objective(s) and endpoint(s):									

  
 Objectives	Endpoints	
   
 Primary	 
 To demonstrate the efficacy of ivosidenib based on PFS status at 6 months per Independent Radiology Center (IRC) assessment Progression-free survival (PFS) status (as assessed by the IRC per Response Evaluation Criteria in Solid Tumors [RECIST] v1.1) at 6 months after Day 1 (C1D1). 	
 
 Secondary	 
 To evaluate the safety and tolerability of ivosidenib AEs, SAEs, AEs leading to discontinuation or death. The severity of AEs will be assessed by the National Cancer Institute Common Terminology Criteria for Adverse Events (NCI CTCAE), version 5.0. Safety laboratory parameters, vital signs, 12-lead ECGs, evaluation of left ventricular ejection fraction (LVEF), Eastern Cooperative Oncology Group (ECOG) performance status (PS), and concomitant medications. 	
 
 	 
 To evaluate the efficacy of ivosidenib on overall survival (OS), progression free survival (PFS), objective response (OR), duration of response (DOR), and time to response (TTR), with response assessed per Investigator and by the IRC. OS, defined as the time from Day 1 (C1D1) to date of death due to any cause. PFS, defined as the time from C1D1 to the date of first documentation of disease progression as assessed by the Investigator and by the IRC per RECIST v1.1. or death due to any cause, whichever occurs first. OR, defined as objective response (confirmed CR or confirmed PR), as assessed by the Investigator and by the IRC per RECIST v1.1. DOR, defined as the time from date of first documented confirmed complete response (CR) or confirmed partial response (PR) to date of first 	
  
		Objectives	Endpoints	Primary	
 To demonstrate the efficacy of ivosidenib based on PFS status at 6 months per Independent Radiology Center (IRC) assessment Progression-free survival (PFS) status (as assessed by the IRC per Response Evaluation Criteria in Solid Tumors [RECIST] v1.1) at 6 months after Day 1 (C1D1). 	Secondary	
 To evaluate the safety and tolerability of ivosidenib AEs, SAEs, AEs leading to discontinuation or death. The severity of AEs will be assessed by the National Cancer Institute Common Terminology Criteria for Adverse Events (NCI CTCAE), version 5.0. Safety laboratory parameters, vital signs, 12-lead ECGs, evaluation of left ventricular ejection fraction (LVEF), Eastern Cooperative Oncology Group (ECOG) performance status (PS), and concomitant medications. 		
 To evaluate the efficacy of ivosidenib on overall survival (OS), progression free survival (PFS), objective response (OR), duration of response (DOR), and time to response (TTR), with response assessed per Investigator and by the IRC. OS, defined as the time from Day 1 (C1D1) to date of death due to any cause. PFS, defined as the time from C1D1 to the date of first documentation of disease progression as assessed by the Investigator and by the IRC per RECIST v1.1. or death due to any cause, whichever occurs first. OR, defined as objective response (confirmed CR or confirmed PR), as assessed by the Investigator and by the IRC per RECIST v1.1. DOR, defined as the time from date of first documented confirmed complete response (CR) or confirmed partial response (PR) to date of first

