Daily study treatment will begin on C1D1. Cycles are 28 days (± 2 days) in duration and dosing is continuous. All subjects will continue to receive best supportive care according to institutional practice throughout the study. Study visits will be conducted every week during Cycle 1 (Days 1, 8, 15, and 22), and every other week during Cycles 2 and 3, and Day 1 of each cycle thereafter.

An End of Treatment (EOT) Visit will be performed on the last day of study treatment (within 5 to 33 days of last dose, to accommodate for potential dosing delays of up to 28 days).

Radiographic assessment (CT or MRI) for evaluation of disease response will be conducted every 6 weeks (± 5 days) for the first 8 assessments (i.e., through week 48) and every 8 weeks (± 5 days) thereafter from C1D1, independent of dose delays and/or dose interruptions, and/or at any time when progression of disease is suspected. For subjects who discontinue study drug

for reasons other than disease progression, than withdrawal of consent, or start of another anticancer agent, an assessment will be conducted at the EOT Visit.

Upon radiographic disease progression, PIs, with consult from the Sponsor, may keep the subjects on ivosidenib after the disease progression provided the subject is clinically benefitting and there is no contraindication to continuing treatment beyond progression (see [Section 8.10.1.2](#)). Target and non-target lesion selection and objective tumor response assessments per Response Evaluation Criteria in Solid Tumors (RECIST) v1.1 will be performed by the Investigator(s). An independent central review of response will be conducted by an Independent Radiology Center (IRC) per RECIST v1.1. All scans will be sent to the IRC as detailed in the site-specific Imaging Core Manual (see [Section 7.2.1](#)). HRQOL assessments will be conducted pre-dose on C1D1 and on Day 1 of every cycle thereafter until EOT. After EOT visit, the HRQOL will be conducted every 12 weeks until the start of new anticancer therapy. One additional HRQOL assessment will also be conducted at the safety follow-up visit. Health economic outcomes assessments will occur pre-dose on C1D1 Cycle 3, Day 1 (C3D1), and at the EOT visit. Compliance assessments will occur at Cycle 2, Day 1 (C2D1), Day 1 of every cycle thereafter, and at the EOT Visit.

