OS follow-up assessments will occur approximately every 12 weeks after EOT unless the subject is in PFS follow-up at that time. If a subject progresses or does not come back for scans while in PFS follow-up, then the OS follow-up assessments will begin at the next planned OS follow-up time point, following the schedule of every 12 weeks. OS follow-up will continue until all subjects have died, withdrawn consent, or are lost to follow-up, or up to 24 months after the last subject enrolled, whichever occurs first.

End of Study: End of study is defined as the time until when all subjects have died, withdrawn consent, lost to follow-up, up to 24 months after the last subject enrolled, or the Sponsor has terminated the study, whichever comes first. Final analysis for OS will be conducted at the end of the study.

[figure not shown]
The study plan is shown in [Figure \(4.1.1\) 1](#).

In case of non-inclusion of a participant, it is the Investigator's responsibility to ensure, in accordance with the local standards of care and medical practices that:

- The reason of non-inclusion is explained to the participant,
- Any event associated with any procedure/condition required by the study protocol (e.g. an event occurring following the discontinuation of a forbidden treatment) is collected,
- An adequate alternative medical care is proposed to the participant.

A non-inclusion visit is not mandatorily carried out, provided these requirements are met and documented in the medical file of the participant.

Figure (4.1.1) 1 - Study plan

If a subject progresses or does not come back for scans while in PFS follow-up, then the OS follow-up assessments will begin at the next planned OS follow-up time point, following the schedule of every 12 weeks.

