10.1.2. Statistical methods

10.1.2.1. General considerations

Summaries will be produced for disposition, demographic and baseline disease characteristics, safety and tolerance, pharmacokinetics, PD biomarkers, and efficacy variables, as appropriate.

Categorical data will be summarized by frequency distributions (number and percentages of subjects). Continuous data will be summarized by descriptive statistics (mean, standard deviation, median, minimum, and maximum). Time-to-event endpoints will be estimated using Kaplan-Meier methods. Point estimates and 95% CIs will be provided where appropriate, and estimates of the median and other quantiles, as well as individual time points (eg, 3-month, 6-month, and 12-month rates) will be produced.

PK data will be provided in by-subject listings.

The study data will be analyzed and reported in the primary clinical study report (CSR) based on all subjects' data up to the time when PFS events have been determined by Investigator assessment in all subjects. Any additional data for survival follow-up and for subjects continuing to receive study treatment past the data cutoff date for the CSR until the end of study will be reported in CSR addendums or the final CSR.

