**1.3. Determination of sample size**

Approximately 10 Japanese subjects will be enrolled in the study.

The primary endpoint is PFS status (as assessed by IRC per RECIST v1.1) at 6 months after Day 1 (C1D1). Assuming a target 6-month PFS rate of 32% and a dropout rate of 10%, the study needs to enroll 10 subjects to provide approximately 84% power to reject the null hypothesis of PFS rate  $\leq 2.6\%$  using exact binomial test at 1-sided significance level of 0.05.

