#### 5.3.1. Primary efficacy endpoint

The primary analysis will be performed on the ITT set.

The progression-free survival (PFS) by IRC is defined as the time in months from Day 1 (C1D1) to the date of the first documentation of disease progression as determined by the IRC per RECIST v1.1 or death due to any cause, whichever occurs first.

PFS = (Earliest Date of Disease Progression or Death – Day 1 Date + 1) / 30.4375.

The primary endpoint is PFS status at 6 months after Day 1 (C1D1). The 6-month PFS rate defined as the probability of subjects who are alive and progression-free at 6 months after Day 1 (C1D1) will be used to assess the primary endpoint. Kaplan-Meier method will be used to estimate the 6-month PFS rate. Exact binomial test with 1-sided significance level of 0.05 will be used to compare the 6-month PFS rate against 2.6%.

Subjects without documentation of disease progression or death at the time of the analysis of PFS will be censored at the date of the last response assessment prior to the start of alternate therapy. See [Table \(5.3.1\) 1](#) for the details on handling of missing response assessments and censoring.

Number of subjects with events, types of events (progression or death), and number of subjects censored, number of subjects for each reason of censoring, Kaplan-Meier estimates, and 95% CIs according to Brookmeyer and Crowley method for the median, Q1 and Q3 for PFS will be presented. Probabilities of event free at selected time points, such as 3-month, 6-month, 9-month, and 12-month, will be presented. Kaplan-Meier curves of PFS will be provided with the number of subjects at risk over time included.

In addition, the concordance of PFS between investigator and IRC assessment will also be summarized.

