**Table (5.3.1) 1 Handling of Missing Response Assessment and Censoring for the Primary Analysis of PFS**

Situation	Date of Censoring
No baseline assessment and no death.	Date of the Cycle 1 Day 1
Alternate anticancer systemic treatment started before documented progression (PD) per RECIST 1.1 or death.	Date of last adequate assessment prior to the start of alternate anticancer treatment 
No adequate post-baseline assessment and no death.	Date of the Cycle 1 Day 1
No documented PD per RECIST 1.1 or death before data cut-off date or before permanently discontinued from the study.	Date of last adequate assessment 

Situation	Date of Censoring
Documented PD per RECIST 1.1 or death following a long gap from the previous adequate assessment (e.g., 2 or more consecutive missed scheduled disease status assessments). The long gap is defined as $\geq 95$ days (ie, 12 weeks + 10 days per the protocol defined visit window). If no adequate assessment prior to minimum of (PD, death), the long gap is calculated from the Cycle 1 Day 1.	Date of last adequate assessment prior to the first occurrence of 2 or more consecutive missing scheduled assessments

 Adequate disease assessment is defined as a response assessment other than “not evaluable.” If there is no adequate response assessment prior to the start of anticancer treatment, it will be censored at the date of Cycle 1 Day 1.

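### The primary analysis is timed 22 to 32 days before the last subject's Week 30 scan, and the exact test has no rule for subjects censored before 6 months

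*SAP*

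**What the plan says.** - **Timing.** SAP Section 1: "The primary analyses will be performed approximately 6 months after the last subject enrolled for the 6-month PFS rate assessment". This is the SAP's only timing for the primary analysis. The censoring table refers to a data cut-off date that is not defined.
- **Scans.** Protocol Section 4.1.1 schedules imaging from C1D1 "every 6 weeks (± 5 days) for the first 8 assessments (i.e., through week 48").
- **Censoring.** One row of SAP Table (5.3.1) 1 covers subjects with "No documented PD per RECIST 1.1 or death before data cut-off date or before permanently discontinued from the study". They are censored at the last adequate assessment, not at the cut-off.
- **Estimate and test.** SAP Section 5.3.1 estimates the 6-month rate by Kaplan-Meier but tests it differently: "Exact binomial test with 1-sided significance level of 0.05 will be used to compare the 6-month PFS rate against 2.6" percent.
- **Sample size.** SAP Section 1.3: "Assuming a target 6-month PFS rate of 32% and a dropout rate of 10%, the study needs to enroll 10 subjects", for about 84% power.
- **A second timing statement.** Protocol Section 10.1.2.1 takes data for the primary study report "up to the time when PFS events have been determined by Investigator assessment in all subjects". SAP Section 7 lists no changes from the protocol.

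**The concern.** The analysis is timed to assess status at 6 months, yet no scheduled scan falls between Day 173 and Day 205. By the SAP's own censoring rule, the last subject's 6-month status is not established when the analysis is due. The same holds for anyone who started within about a month before that subject.

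This is a consequence of the censoring convention, not of lost progression data. Once the Week 30 scan is done, the subject's PFS time is 6.8-7.1 months even if that scan shows progression.

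Kaplan-Meier can use a time censored at 5.5 months; an exact binomial test cannot. The SAP treats subjects without a response assessment as non-responders for objective response (Section 5.3.2.3), but it gives no matching rule for the primary endpoint. Left open, the choice between success, non-success and exclusion would be made with the data in view, in an open-label trial of ten subjects. The same gap affects dropouts and subjects censored for new therapy or long assessment gaps, whatever the cut-off.

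**Working it through.** **The plan's own power.** Under the null rate of 2.6%, P(X ≥ 2) is 0.0265 for n = 10 and 0.0216 for n = 9. P(X ≥ 1) is 0.2316 and 0.2111. The pass mark is therefore 2 successes, and it stays at 2 for every n from 2 to 10 (at n = 2, P(X ≥ 1) = 0.0513). At a true rate of 32%, P(X ≥ 2) is 0.837 for n = 9 and 0.879 for n = 10. The stated 84% thus corresponds to 9 evaluable subjects, that is, 10 less 10% dropout.

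**Dates** (days after C1D1; the SAP formula adds 1 and divides by 30.4375).
- 6 months: 6 × 30.4375 = 182.6 days.
- Week 24: 168 ± 5 = Day 163-173. PFS time is 164/30.4375 = 5.39 to 174/30.4375 = 5.72 months.
- Week 30: 210 ± 5 = Day 205-215. PFS time is 206/30.4375 = 6.77 to 216/30.4375 = 7.10 months.
- Gap from 6 months to Week 30: 205 − 182.6 = 22.4 days to 215 − 182.6 = 32.4 days.

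**Loss without an accrual assumption.** Count dropouts as non-successes, so p = 0.32 × 0.9 = 0.288. Any cut-off before Day 205 leaves at least the last subject without a Week 30 scan. Suppose that subject is a non-success or is excluded; the two are equivalent here because the pass mark stays at 2.
- All 10 with status: 1 − 0.712^10 − 10 × 0.288 × 0.712^9 = 0.831.
- Last subject lacking: 1 − 0.712^9 − 9 × 0.288 × 0.712^8 = 0.782.
- Two lacking: 1 − 0.712^8 − 8 × 0.288 × 0.712^7 = 0.720.
- Verdict changed when only the last subject is affected: 0.288 × [9 × 0.288 × 0.712^8] = 0.049.

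**Loss with assumed accrual.** Accrual length is not stated. The protocol synopsis gives a September 2023 start and "Study completion date: Estimated May 2027"; Section 4.1.1 runs survival follow-up "up to 24 months after the last subject enrolled, whichever occurs first". May 2027 less 24 months is May 2025, about 20 months after the start. Simulations used 400,000 trials per case, scan timing uniform within ± 5 days, enrolment taken as C1D1 and the same counting rule. At a Day 183 cut-off:

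| Assumed accrual | Power | Verdict changed | Mean subjects without Week 30 |
|---|---|---|---|
| Evenly spaced, 20 months | 0.781 | 0.049 | 1.00 |
| Front-loaded, 20 months | 0.765 | 0.067 | 1.27 |
| Uniform, 20 months | 0.754 | 0.077 | 1.44 |
| Uniform, 12 months | 0.732 | 0.098 | 1.74 |
| Back-loaded, 20 months | 0.730 | 0.103 | 1.82 |
| Uniform, 6 months | 0.677 | 0.155 | 2.48 |

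**Later cut-offs** (uniform, 20 months): Day 197 gives 0.769, Day 204 0.777, Day 210 0.806 and Day 215 0.832.

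**Other checks** (uniform, 20 months). Carrying Week 24 status forward at Day 183 gives 0.832, so no loss. Under the null, rejection is 0.016 at Day 183 and 0.022 at Day 215. The mean Kaplan-Meier 6-month rate was 31.2% against 31.5%. That last pair depends on the event-time model, which the documents do not give, so it is only indicative.

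**The case against.** - **The timing is only approximate.** The sentence says when analyses are performed, not where data are cut, and Day 215 is 7.1 months. A team that waits loses nothing. This stands as a description of what could happen, but nothing requires the wait, and Day 204 still gives only 78%.
- **The protocol may already resolve it.** If Section 10.1.2.1 governed, administrative censoring would largely disappear. However, that section concerns the study report, refers to the Investigator although the endpoint is read by the IRC, and gives no counting rule. Its meaning is also uncertain: determined may mean status known rather than an event in every subject. The mismatch may be version lag, since SAP 1.0 is tied to protocol 1.0 with amendments 1 to 3 and the protocol at hand was signed in May 2024.
- **The loss comes from an assumed counting rule.** This is correct. A subject alive without IRC progression at Day 183 could reasonably be called progression-free, and then the loss is zero. The SAP does not say so, and its table censors that subject before 6 months.
- **The Week 30 scan tells little about 6-month status,** because it yields a success whether or not it shows progression. That is fair. Its value is that status then follows from the existing censoring table.
- **The 84% already allows for one subject in ten without status.** True: with no dropouts, one late enrolee takes power from 87.9% to 83.7%. The 78.2% applies when the loss comes on top of the dropout allowance.
- **The error is conservative.** Also true: under the adverse rule a success can be lost but none is created. When only one subject is affected, about 95% of verdicts are unchanged (1 − 0.049).

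**Conclusion.** The concern holds. Followed as written, the plan leaves at least the last subject, if event-free, censored at 5.4-5.7 months, with no stated way to enter the exact test. The missing counting rule is a defect at any cut-off; the early timing adds subjects to whom it applies.

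The loss ranges from nothing (Week 24 status carried forward) to about 8 points of power at 20 months' uniform accrual, and more if accrual is faster. The accrual-free figures, power of at most 78.2% and a changed verdict in at least 4.9% of trials, rest on four assumptions: a cut-off before Day 205, late enrolees counted as non-successes or excluded, the SAP's 32% and 10% inputs, and no unscheduled scan after 6 months. If enrolment precedes C1D1, the gap to Week 30 is longer. Type I error is not inflated. The point should be fixed, but it does not undermine the design.

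**What to change.** 1. **One cut-off, in SAP Section 1 and Protocol Section 10.1.2.1.** Suggested wording: *The data cut-off is Day 215 after C1D1 of the last treated subject, or earlier once every treated subject has had the Week 30 scan or has had IRC progression, died, started new anticancer therapy, stopped tumour assessments or left the study. All scans to that date are read by the IRC before the analysis.*
2. **A counting rule, in SAP Section 5.3.1, fixed before the data are analysed.** Suggested wording: *The denominator is all ITT subjects. A success is a PFS time, event or censored, of at least 6 months. A subject censored before 6 months is not a success; numbers and reasons are reported.*

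The second change is needed at any cut-off. The first keeps it from costing power through late enrolment. If the sponsor will not wait, the alternative is to pre-specify that Week 24 status is carried forward for subjects alive without IRC progression at 6 months. That also gives 83%, but it counts as successes subjects whom Table (5.3.1) 1 censors at 5.4-5.7 months.

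The cost is wording in two documents and a primary readout about one month later (215 − 183 = 32 days). No extra scans or patients are needed.
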